On each of the intervention dates, women of childbearing potential will undergo urine β -hCG testing, and will be excluded if pregnancy test is positive. Participants will complete a brief pain assessment, as well as WUR and CPM testing at baseline (Figure 2B). Thereafter, two IV catheters will be inserted in participants' arms. One will be utilized for drug infusion and the catheter in the contralateral arm will be used for serial blood sampling. One 5-ml blood sample will be obtained for P-glycoprotein polymorphism analysis. At study visit 1 and study visit 2, an additional 5-ml baseline blood sample will be obtained for future research with participant consent. Participants will report baseline spontaneous pain (0-10 NRS) and complete a baseline NPSI. Placebo (D5W solution) or tariquidar (4mg/kg dose) will be administered IV over 60 minutes. Starting 30 minutes after the initiation of tariquidar/placebo, a 15-min ondansetron co-infusion will be given, infused via Y-site, to time its peak brain concentration with Pgp inhibition. The intensity of spontaneous pain (on 0-10 NRS) will be assessed every 10 minutes for 60 minutes, and every 15 minutes thereafter for a total of 120 minutes, then every 30 min for a total of 240 minutes. WUR and CPM testing will be repeated 90 minutes after the end of ondansetron infusion (i.e., 105 minutes after the beginning of ondansetron infusion). Participants will record self-reported pain hourly on the study day until bedtime, and daily for 3 weeks thereafter. NPSI pain descriptors will be assessed prior to, and 70 minutes after, the beginning of ondansetron infusion. Additionally, blood samples for ondansetron concentrations will be obtained at baseline (time zero) and approximately at 15, 30, 60, 90, 120, 180, and 240 minutes from the beginning of ondansetron

infusion (See Table 1 for full summary of the measurement schedule.) Plasma will be processed and stored in aliquots at -80°C until analysis. A 3-mL CSF sample (per participant's consent) will be obtained via lumbar puncture between 30 and 180 minutes from the beginning of ondansetron infusion, for the assessment of ondansetron concentration in the CSF using population PK approach as we previously described³¹. Lumbar puncture will not be performed if participant is currently taking anticoagulant treatment or if the participant has a contraindication to the lumbar puncture per investigator discretion.

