2.4.5.2 Secondary Outcome Measures

Secondary outcome measures include:

1. Change in spontaneous pain intensity (measured on 0-10 NRS) from baseline to 60-120 minutes after ondansetron IV infusion, compared between two sessions with and without tariquidar. The pain severity values obtained at 60, 90, and 120 minutes will be averaged to derive the secondary outcome measure. The values will be compared via paired t-test (or Wilcoxon signed-rank test, if data not normally distributed).
2. Changes in NPSI total score and sub-scores (burning pain, paroxysmal pain, paresthesia/dysesthesia score) will be compared between treatment sessions;
3. The association between baseline Conditioned Pain Modulation (CPM) magnitude (Δ CPM) and the % pain reduction from baseline will be determined by bivariate regression. A significant association between the two measures will be indicative of differential analgesic response as a function of descending pain modulation;

Exploratory analyses will be performed to determine if variables such as sex, weight, baseline wind-up ratio (WUR), peak ondansetron plasma concentration, and P-glycoprotein genotype affect the difference in pain reduction between the two study sessions.

A population PK approach will be used to model CSF concentrations of ondansetron with and without tariquidar co-administration.

Table 1. Study Day Timeline

	Drug	Blood*		PK		NRS	NPSI	CPM	WUR	QST	Questionnaires
Screening	TQD	OND	X	Blood	CSF	X	X	X	X	X	X
Study day (min after ondansetron infusion start)											
Baseline			X	X		X	X	X	X	X	
-30 min	TQD / placebo Infusion										
0 min		OND infusion		X		X					
10 min						X					
15 min				X							
20 min						X					
30 min				X	X**	X					
40 min						X					
50 min						X					
60 min				X		X					
70 min							X				
75 min						X					
90 min				X		X					
105 min						X		X	X		
120 min				X		X					
135 min						X					

150 min						X					
165 min						X					
180 min				X		X					
240 min				X		X					
Hourly after discharge- study day						X					
Post-study day (weeks)											
1						daily					
2						daily					
3			X			daily					

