Determination of wind-up ratio (WUR)

Equipment: A standardized weighted metal probe (Nervetest, MRC systems) exerting pressure of 256 mN.

Methods and Background:

Wind-up ratio (WUR) to punctate mechanical stimulation (i.e. temporal summation) will be measured as another surrogate of descending facilitation. WUR will be assessed by a published protocol.^{32,36} In this test a 256mN pinprick probe (Nervetest, MRC systems, Germany) is first applied singularly and then as a series of 10 identical stimuli with 1Hz frequency within an area of 1 cm². Immediately following the single and 10 stimuli, participants rate their pain on a 0-10 NRS, and a ratio is calculated using these values. This procedure is repeated twice; a geometric 'wind-up' average is calculated from the two ratios.

Determination of conditioned pain modulation (CPM)

Equipment: A thermostat-controlled digital water bath; The Thermal Sensory Analyzer (TSA-II platform - Medoc, Ramat Yishai, Israel)

Methods and Background:

Conditioned pain modulation (CPM) is a surrogate measure of descending inhibition vs. facilitation. CPM efficiency is derived from a patient report of pain intensity following application of a calibrated painful stimulus (called test stimulus) with and without another ongoing unpleasant stimulus (called conditioning stimulus). The intensity of the conditioning and pain stimulus will be determined individually by cold temperature that elicits pain intensity of 30-70 on 0-100 NRS (conditioning), and hot temperature that elicits pain intensity of 60 on 0-100 NRS (test).

The conditioning stimulus will be applied by immersing the non-dominant or non-affected arm in a cold thermostat-controlled water bath. The initial temperature will be set to +8°C. If that temperature elicits pain intensity between 30-70 on 0-100 NRS, the CPM protocol will use +8°C conditioning. Alternatively, water temperature will be adjusted in 2°C increments (lowest will be 2°C) to elicit pain in that range.

The previously determined Pain-60 test stimulus will be applied at the dominant or affected forearm, using a 3x3 cm Peltier thermode connected to TSA-sensory analyzer (Medoc Inc, Ramat Yishai, Israel).

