The length of the conditioning is 60 seconds; during the last 30 seconds, the test stimulus is applied. The difference between test stimulus intensity with and without conditioning is defined as CPM magnitude. CPM>0 (i.e. increased pain to test stimulus following conditioning) implies descending pain facilitation.^{37,38}

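### Baseline pain is rated after the painful CPM and WUR tests, so any carry-over from CPM would bias the regression of % pain reduction on CPM towards the study's hypothesis

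*Combined protocol and SAP*

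**What the plan says.** Section 2.4.3 (Study Period) sets out each intervention day as a sequence: "Participants will complete a brief pain assessment, as well as WUR and CPM testing at baseline (Figure 2B). Thereafter, two IV catheters will be inserted". Blood samples come next, and then: "Participants will report baseline spontaneous pain (0-10 NRS) and complete a baseline NPSI. Placebo (D5W solution) or tariquidar (4mg/kg dose) will be administered". The text gives no rest period between the tests and these ratings.

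Table 1 neither confirms nor corrects this order. Its study-day Baseline row holds NRS, NPSI, CPM, WUR and QST together without a sequence. Study-day QST does not appear in 2.4.3. Table 1 also has an NRS at 0 minutes, which is 30 minutes into the tariquidar or placebo infusion.

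In 2.4.6, the CPM test combines heat set to a pain level of 60/100 with cold water set to 30-70/100, and WUR uses repeated 256 mN pinpricks. On the sign of the predictor: "CPM>0 (i.e. increased pain to test stimulus following conditioning) implies descending pain facilitation".

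Secondary outcome 3 (2.4.5.2) says that the association between baseline CPM "magnitude (Δ CPM) and the % pain reduction from baseline will be determined by bivariate regression", and it treats a significant association as evidence of differential analgesic response. The pain outcome averages the NRS at 60, 90 and 120 minutes. CPM and WUR are repeated at 105 minutes.

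**The concern.** The baseline NRS is both the reference and the denominator of % pain reduction. If the CPM test leaves spontaneous pain somewhat higher in patients who facilitate and lower in those who inhibit, recorded baselines move with CPM. As the effect fades before 60 minutes, facilitators appear to improve more and inhibitors less, with no drug involved. Section 2.1 expects the drug to work in patients with descending facilitation, so the artefact would look like the hypothesised result. Once the data are collected in this order, it cannot be separated from a true association.

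**Working it through.** **Inputs from the documents.** n = 28; baseline pain 6.3 (SD 2.1); post-dose pain SD 2.1, with means 5.1 (ondansetron + placebo) and 4.0 (ondansetron + tariquidar); two-tailed 5% level (2.4.7). Entry requires NRS of at least 4 (2.3.2). The plan gives no figure for the CPM regression, so there is none to reproduce.

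**Assumed.** The carry-over k, in NRS points per SD of CPM. The documents give no value; 0.25 and 0.5 are illustrations.

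**Step 1: size of the artefact.** Let B be baseline, P the averaged post-dose rating, and R = 100 × (1 − P/B).
- Baseline only shifts: dR/dB = 100 × P/B² = 100 × 5.1/6.3² = 12.8 percentage points per NRS point. The false slope is about 3.2 points per SD of CPM at k = 0.25 and 6.4 at k = 0.5.
- The repeat test at 105 minutes also shifts the 120-minute rating by k. One third of the average moves, which removes 100 × (k/3)/6.3 = 1.3 points at k = 0.25 and 2.6 at k = 0.5. The net slope is about 1.9 and 3.8.

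**Step 2: residual SD for the simulation.** Baseline N(6.3, 2.1) restricted to 4-10 has SD 1.49. With a true 20% reduction, P = 0.8B + error, so the post-dose SD is √((0.8 × 1.49)² + s²).
- s = 1.0 gives 1.55, below the stated 2.1.
- s = 1.65 gives 2.03, close to the stated 2.1.
- Matching 2.1 exactly needs s = √(2.1² − 1.19²) = 1.73.

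**Step 3: false-positive rate.** No true CPM association; a single session's % reduction regressed on standardised CPM; s = 1.65.

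| k (NRS points per SD of CPM) | Baseline only shifts | 120-min rating shifts equally |
|---|---|---|
| 0 | about 5% | about 5% |
| 0.25 | about 9% | about 6% |
| 0.5 | about 21% | about 10% |

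Repeat runs agree to within one or two percentage points. A second error model (post-dose SD 2.1, pre/post correlation 0.5 or 0.7) gives 8-10% and 18-27% with the baseline shift only, and 6-7% and 9-13% with the 120-minute shift. At k = 0.5, nearly all false positives lie in the hypothesised direction.

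**Step 4: the between-session comparison.** Suppose that baseline is 7.3 instead of 6.3 in both sessions, with post-dose pain unchanged.
- Apparent reduction with ondansetron + placebo: 1 − 5.1/6.3 = 19.0% becomes 1 − 5.1/7.3 = 30.1%.
- Apparent reduction with ondansetron + tariquidar: 36.5% becomes 45.2%.
- Difference in absolute change: 2.3 − 1.2 = 1.1 becomes 3.3 − 2.2 = 1.1, so it does not move.

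**Step 5: reordering alone.** If baseline is rated before the tests but the 120-minute rating stays in the average, the slope becomes about −1.3 (k = 0.25) or −2.6 (k = 0.5). The rejection rate is about 5% and 8%, now mostly against the hypothesis. The fix therefore has to cover the 120-minute value.

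**The case against.** The mechanism is a conjecture. CPM is defined on pain from the heat stimulus, not on spontaneous neuropathic pain, and nothing in the documents shows an effect that outlasts the test, the cannulation and the blood draws. With no carry-over the test keeps its 5% level. This stands, and it is why the point is about a possible bias.

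The order is not beyond doubt either. The word that fixes the sequence governs only the catheters; the place of the ratings follows from sentence order, and the testing-day figure is not visible in the text available. A brief pain assessment of undefined content is also listed alongside the tests. Sentence order is still the plain reading, and nothing visible contradicts it.

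The predictor might be the screening CPM. If screening is on another day, the link is indirect. But the plan does not say which CPM is used, and 2.4.3 allows screening on the morning of test day 1.

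A reader might infer three stronger things that the documents do not support:
- That false-positive rates reach 50%. At k = 0.5 this needs a residual SD of 1.0, which implies a post-dose SD below the stated one, and it ignores the repeat CPM at 105 minutes.
- That all pain outcomes are compromised. The same sequence is used in both sessions, so the paired comparisons largely cancel the shift.
- That the reference rating is contradictory. Table 1 separates Baseline from 0 minutes, and the time-zero wording in 2.4.3 concerns blood samples. Naming the reference rating is a clarification.

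**Conclusion.** The point holds for one analysis, the regression of % pain reduction on CPM. As 2.4.3 is written, a painful test that measures the predictor comes before the denominator of the outcome, with no stated recovery, and any CPM-related carry-over would favour the hypothesis. The size depends on an assumed carry-over. For 0.25 to 0.5 NRS points per SD of CPM and a residual SD roughly matching the stated post-dose SD, false positives are about 9-21% if only the baseline shifts and about 6-10% if the repeat test shifts the 120-minute rating equally. The NRS and NPSI comparisons between sessions are largely protected, provided that carry-over is similar in the two sessions. The sample size is not affected. The change is worth making because it costs little and the bias could not be removed afterwards.

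**What to change.** In 2.4.3 and Table 1:
- Record the baseline NRS and NPSI first on each test day, together with the brief pain assessment already listed, before WUR, CPM, any QST and cannulation. Name that rating as the reference for all pain outcomes.
- Keep the 0-minute NRS as descriptive only.
- Reconcile the study-day QST entry in Table 1 with 2.4.3, which does not mention it.

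In 2.4.5.2:
- State whether the screening or the test-day CPM is the predictor.
- Add a CPM regression that omits the 120-minute NRS, since that rating follows the repeat CPM and WUR at 105 minutes.

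No procedure is added. The cost is a longer gap between the baseline rating and the infusion, which the 0-minute NRS can describe, and one fewer rating in the average for the added analysis. Any effect of testing or cannulation that lasts to 60 minutes would then count as change from baseline, but it would occur in both sessions.

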2.4.4 Minimization of Bias

There will be no specific ethnic, racial, or gender background for enrollment. The study is designed as cross-over in order to minimize inter-subject variability. The participants and investigators will be blinded to treatment allocation sequence.

2.4.5 Observations and Measurements

2.4.5.1 Primary Outcome Measures

Primary outcome:

The primary objectives are to evaluate the pharmacokinetics and the tolerability of ondansetron and tarividar single dose iv co-administration (in comparison to ondansetron administration alone) in patients with neuropathic pain.

Pharmacokinetics:

-Venous blood sampling for pharmacokinetics will be obtained: at 0, 15, 30, 60, 90, 120, 180, and 240 minutes from the beginning of ondansetron infusion.

-A CSF sample will be obtained via lumbar puncture between 30 and 180 minutes from the beginning of ondansetron infusion, for the assessment of ondansetron concentration in the CSF using population PK approach.

-CSF to plasma ratio of ondansetron will be calculated, and compared between the two study arms

Tolerability:

-Spontaneous reporting of adverse effects

- Vital signs (pulse oximetry, blood pressure): before infusion and 30, 60, 120, 180 and 240 minutes after end of ondansetron infusion.
- 12-lead ECG: At baseline and prior to discharge after each treatment session.
- Troponin T: at screening and prior to discharge after each treatment session.
- Blood chemistry (CMP) and count (CBC) at baseline and at 3-week time point after each treatment session.
- In patients who are concomitantly treated with SSRI or SNRI medications that are allowed for inclusion (duloxetine ≤60mg/day, citalopram ≤20mg/day, or Escitalopram ≤10mg/day, additional assessments will be performed at the time of vital sign assessments (baseline and 30, 60, 120, 180 and 240 minutes after end of ondansetron infusion) to evaluate confusion, restlessness, dilated pupils, muscle twitching or rigidity, and sweating. This will be performed to identify signs suggestive of serotonin syndrome.

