In addition, a series of experiments were performed to determine the concentration of ondansetron in rat CSF, spinal cord, and brain, performed in wild-type rats, with and without intravenous 7.5mg/kg tariquidar co-administration.

- Plasma to CSF partition coefficient (Cp) of ondansetron, after 10mg/kg dose, in wild-type male rats without tariquidar was 0.27 ± 0.3 ; plasma to CSF partition coefficient (Cp) of ondansetron, with co-administration of 7.5mg/kg tariquidar was 0.36 ± 0.16
- Plasma to spinal cord partition coefficient (Cp) of ondansetron, after 10mg/kg dose, in wild-type male rats without tariquidar was 1.11 ± 0.4 ; plasma to spinal cord partition coefficient (Cp) of ondansetron with co-administration of 7.5mg/kg tariquidar was 4.72 ± 2.8
- Plasma to brain partition coefficient (Cp) of ondansetron, after 10mg/kg dose, in wild-type male rats without tariquidar was 1.75 ± 1.2 ; plasma to brain partition coefficient (Cp) of ondansetron with co-administration of 7.5mg/kg tariquidar was 5.88 ± 5.6

In summary, co-administration of tariquidar resulted in 1.3 fold increase in CSF to blood partitioning coefficient, while in parallel, spinal cord to blood partitioning coefficient increased 4.2-fold, and brain to blood partitioning coefficient increased by 3.4-fold.

Cardiovascular safety data from the first 8 participants in the human pharmacokinetic study per IND 140361 (NCT03809234; 2 participants with 4mg ondansetron, 4 participants with 8mg ondansetron, and 2 participants with 16 mg ondansetron, with and without 4mg/kg tariquidar) demonstrate the following:

- None of the participant had any increase in troponin at any point in the study.
- The QTc interval changes (before to after ondansetron) with and without tariquidar were -2.5 ± 16.1 ms vs 2.9 ± 13.1 ms, respectively (non-significant difference).
- Maximum change in systolic blood pressure was an 8.6 ± 9.7 mmHg increase, two hours after infusion of ondansetron with placebo, and a 5.7 ± 8.2 mmHg decrease, 1.5 hours after infusion of ondansetron with tariquidar, across doses.
- Maximum change in diastolic blood pressure was an 3.4 ± 7.7 mmHg increase, two hours after infusion of ondansetron with placebo, and an 7.1 ± 9.6 mmHg increase, 105 minutes after infusion of ondansetron with tariquidar, across doses.

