- Maximum change in heart rate was an 4.2 ± 13.1 BPM increase, 2 hours after infusion of ondansetron with placebo, and an 12.1 ± 17.0 BPM increase, 105 minutes after infusion of ondansetron with tariquidar, across doses.

The CSF concentrations of ondansetron have been analyzed only in the 8mg dose group.

[figure not shown]

Figure 3. CSF concentrations of ondansetron 8mg iv infusion (over 15 min) with and without concomitant administration of 4mg/kg tariquidar (TQD) in healthy volunteers, (0-4 hours). The area under the concentration time curve (AUC₀₋₄) is 14.1 ng*h/mL for ondansetron administered with placebo (D5W solution), and 28.0 ng*h/mL for ondansetron administered with tariquidar.

Based on rodent data, we expect that the increase in spinal cord and brain exposure with tariquidar co-administration will be higher than the proportionate CSF exposure. However, we don't expect as high as 3-4 fold higher exposure in humans, as Pgp expression in rat blood-brain barrier is substantially higher than in humans.

The tolerability and pharmacokinetic parameters of ondansetron co-administered with tariquidar among patients with neuropathic pain is unknown, and should be evaluated before large-scale efficacy clinical studies.

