2.4.3 Study Period

Participants will be studied in the Washington University Pain Center, or in the Clinical Research Unit (CRU) of Washington University School of Medicine, with continued presence of research and nursing personnel. The study will comprise three sessions over an approximately 28-day period (Figure 2A). As previously described, the screening visit will take place within about 7 days prior to the first study visit. The screening visit can be coordinated on the same morning as test day 1.

Intervention:

Each participant will receive two IV infusions of ondansetron, 3 weeks apart, in randomized order. Placebo (D5W) or tariquidar (4mg/kg dose in D5W) will be administered IV over 60 minutes according to randomization schedule. Ondansetron will be diluted in 100mL D5W, and tariquidar will be diluted in 500mL D5W. Starting 30 minutes after the initiation of tariquidar/placebo, a 15-min ondansetron co-infusion will be given, to time its peak brain concentration with potent Pgp inhibition (Figure 3). A 3 weeks interval between the two sessions (> 5 half-lives) will allow the elimination of the first dose of ondansetron and tariquidar. A 12-lead ECG will be repeated prior to the second infusion to confirm that subjects still have a normal QTc and sinus rhythm. Any subject who has a QTc>450ms will not receive the second ondansetron dose and will be withdrawn from the study. A blood sample will be drawn at the 240 min time point for troponin levels. If troponin levels are elevated, the patient will be immediately evaluated by a physician and a cardiology consult will be obtained. Further assessment and treatment of these subjects is described below in section 3, "Management of Intercurrent Events".

Vital signs (pulse oximetry and 3-lead ECG; non-invasive blood pressure) will be monitored before infusion and approximately 30, 60, 120, 180 and 240 minutes after end of ondansetron infusion. A 12-lead ECG will be performed at baseline and before the participants are discharged.

Adverse effects will be collected by spontaneous participant reporting, but also asked about every 30 minutes.

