3.5.5 Potential risks from tariquidar

Tariquidar is an experimental drug, a specific 3rd generation inhibitor of P-glycoprotein, currently in development by Avaant Pharmaceuticals Inc. In a Phase I study in healthy volunteers, intravenous tariquidar doses in the range of 0.1-2mg/kg did not cause any adverse effects.⁴¹

In healthy volunteers, a 2mg/kg intravenous dose resulted in no serious adverse effects. Two of ten subjects receiving this dose developed mild metallic taste during tariquidar infusion. Two subjects who received a 4mg/kg dose experienced light-headedness and conjunctival infection. One subject developed a brief syncopal episode after a PET-scan procedure, resolved without sequelae. A 6mg/kg intravenous dose resulted in mild metallic taste and nausea that resolved after the infusion was stopped.⁴²

In healthy volunteers receiving 4, 6 or 8mg/kg intravenous tariquidar doses, no serious adverse events have been observed.⁴³ Overall, four cases of hematoma and one case of phlebitis due to cannulation, as well as five cases of metallic taste in the mouth occurred. Other adverse drug effects to tariquidar were vertigo (two), bradycardia (one) and headache (one). Heart rate, blood pressure as well as ECG did not significantly change during and after tariquidar administration. No subject had any significant change in blood chemistries (including electrolytes, liver and renal function tests), complete blood count and coagulation over the whole study period. No volunteer discontinued prematurely the study. In one case, for safety reasons the infusion was stopped 20 min before the scheduled end due to moderate orthostatic hypotension and vertigo.⁴³

In an additional healthy volunteer study testing intravenous tariquidar doses in a range of 3-8 mg/kg, adverse events possibly/probably related to tariquidar included 1) dysgeusia (changes in the sense of taste) in 6/20 subjects, across 3mg/kg, 4mg/kg, 6mg/kg and 8 mg/kg doses; 2) vertigo in 3/20 subjects receiving 3mg/kg (n=1) and 8mg/kg (n=2) doses; 3) headache (n=1, 6mg/kg dose); and 4) hypotension and bradycardia (n=1, 8mg/kg; infusion stopped after 7.2mg/kg was infused).

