3.6 Procedures to Minimize Potential Risks

Drug infusions will be administered in the Washington University Clinical Research Unit under the supervision of the PI and the co-investigators. Subjects will be monitored by study personnel during infusions, and dedicated RN personnel is available 24-hours a day on site.

Inclusion and exclusion criteria, monitoring, and the clinical protocol are designed to ensure that risks are absolutely minimal. Participants are informed that participation is voluntary and they may refuse to participate and may withdraw from the study at any time without penalty. A pregnancy test will be performed on women of childbearing potential and subjects excluded if pregnant. Subjects will be told that in the event of a physical injury as the direct result of study procedures, they will be cared for by a member of the investigating team at no cost, within the limits of the Washington University compensation plan.

Subjects will be instructed at the beginning of the visit that they can alert the investigator any time they experience bothersome side effects. In particular, they will be instructed to immediately report palpitations or dizziness/lightheadedness. Continuous physiologic monitoring (ECG, pulse oximetry, and intermittent non-invasive blood pressure) will be used from the beginning of drug infusion until 2 hours after ondansetron infusion is complete. Medical personnel will be immediately available throughout the visit. The subject can voluntarily withdraw from the study at any time.

With regard to confidentiality; 1) all subjects will be assigned a study ID number, 2) Samples will be kept

confidentially. They will be coded, with a key to the code linking code numbers to names kept at a separate location, under lock and key. 3) The link to identifiers will be destroyed at the end of the study. 4) Data will be stored under lock and key (office, file cabinet) and only the investigators and research team will have access. If data are published, there will be no link to identifiers. Study data will not be revealed to any organization, individuals other than the subjects, or the subjects themselves. 5) Study data will not be entered in subjects' medical records.

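### The scheduled vital signs for the primary tolerability outcome include no reading during either infusion, do not name heart rate, and leave the values from the monitor already running outside the outcome.

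*Combined protocol and SAP*

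**What the plan says.** Section 2.4.5.1 makes tolerability, compared with ondansetron alone, part of the primary objective. It lists among the measures "Vital signs (pulse oximetry, blood pressure): before infusion and 30, 60, 120, 180 and 240 minutes after end of ondansetron infusion". The synopsis gives the same times. Section 2.4.3 repeats them as approximate and adds a 3-lead ECG: signs "will be monitored before infusion and approximately 30, 60, 120, 180 and 240 minutes after end of ondansetron infusion". Table 1, which Section 2.4.3 cites as the summary of the measurement schedule, has no vital-sign column.

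On the infusions, Section 2.4.3 says that placebo or tariquidar "will be administered IV over 60 minutes according to randomization schedule". Ondansetron starts 30 minutes into that infusion and lasts 15 minutes.

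Section 3.6 separately describes safety monitoring: continuous ECG and oximetry, with intermittent blood pressure, which "will be used from the beginning of drug infusion until 2 hours after ondansetron infusion is complete". It gives no blood pressure interval and does not say that the values are recorded as outcome data or compared between sessions. Section 2.4.3 also has adverse effects asked about every 30 minutes.

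**The concern.** The experimental component is tariquidar, and the comparison of interest is the session with it against the session without it. If a haemodynamic effect appears while tariquidar is running, or when the two drugs overlap, a schedule that first looks after both infusions have ended will not show it.

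The protocol gives reasons to look there. Section 3.5.5 reports a healthy volunteer in whom "the infusion was stopped 20 min before the scheduled end due to moderate orthostatic hypotension and vertigo", and another infusion stopped early for hypotension and bradycardia. Section 2.2 states that tolerability in patients should be established before large efficacy studies, so a description limited to the period after the infusions would be an incomplete basis for that step.

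Heart rate adds to the concern. It is not on the Section 2.4.5.1 list, yet it triggers a dose-limiting toxicity (Section 3.2) and withdrawal (Section 3.3).

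**Working it through.** **Inputs.** Tariquidar/placebo lasts 60 min; ondansetron starts at minute 30 and lasts 15 min; readings are at 30, 60, 120, 180 and 240 min after ondansetron ends (all Section 2.4.3).

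**Clock check.** Time from ondansetron start = time after its end + 15. Section 2.4.3 equates 90 min after the end with 105 min after the beginning; 90 + 15 = 105, so the plan's own conversion is reproduced.

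**Where the readings fall.** Time from tariquidar start = time after ondansetron end + 15 + 30. Time after tariquidar end = that figure − 60.

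| After ondansetron end | From ondansetron start | From tariquidar start | After tariquidar end |
|---|---|---|---|
| 30 | 45 | 75 | 15 |
| 60 | 75 | 105 | 45 |
| 120 | 135 | 165 | 105 |
| 180 | 195 | 225 | 165 |
| 240 | 255 | 285 | 225 |

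The number of post-baseline readings in minutes 0–60 from tariquidar start is zero, so none falls in the ondansetron infusion (minutes 30–45) either.

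**Meaning of the pre-infusion reading.** Section 2.4.5.1 restates the same times for the serotonin-syndrome checks: "additional assessments will be performed at the time of vital sign assessments (baseline and 30, 60, 120, 180 and 240 minutes after end of ondansetron". The first reading is thus baseline, and in Table 1 the baseline row precedes the tariquidar row. If it instead meant before ondansetron, it could itself be taken during tariquidar, and minutes 30–60 of that infusion would still have no reading.

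**Monitoring window.** Section 3.6 runs from minute 0 to 45 + 120 = 165 min from tariquidar start, so it spans the whole gap.

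**Pilot peak times (Section 2.2).** Tariquidar-session maxima were a "5.7 ± 8.2 mmHg decrease, 1.5 hours after infusion of ondansetron with tariquidar, across doses" for systolic pressure, +7.1 ± 9.6 mmHg at 105 min for diastolic pressure, and a "12.1 ± 17.0 BPM increase, 105 minutes after infusion of ondansetron with tariquidar, across doses" for heart rate. All three placebo-session maxima were at 2 hours. Distance to the nearest scheduled reading depends on the time origin:

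| Maximum | Pilot times from ondansetron end | Pilot times from ondansetron start |
|---|---|---|
| Systolic, tariquidar (90 min) | 30 min | 15 min |
| Diastolic and heart rate, tariquidar (105 min) | 15 min | 30 min |
| All placebo (120 min) | 0 min | 15 min |

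**Strength of the pilot evidence.** Taking n = 8 and ± as SD, t = mean ÷ (SD/√8):
- systolic: 5.7 ÷ (8.2/2.83) = 1.97
- diastolic: 7.1 ÷ (9.6/2.83) = 2.09
- heart rate: 12.1 ÷ (17.0/2.83) = 2.01

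All are below the two-sided 5% critical value of 2.36 on 7 degrees of freedom, before any allowance for having picked the largest of several times.

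**Size of any loss.** This needs the shape of the response, which the documents do not give. Assume a triangular response of half-width h, so that a reading d minutes from the peak captures max(0, 1 − d/h). For h = 30, 60 and 90 min, a peak 15 min away is captured at 50%, 75% and 83%, and a peak 30 min away at 0%, 50% and 67%. The range is too wide to support a figure.

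**The case against.** The strongest reply is that the period is well covered. Section 3.6 and the telemetry in Section 3.6.1 run throughout it. Adverse effects are asked about every 30 minutes, and adverse-effect reporting is itself a primary tolerability item. Section 3.1 has each event recorded with onset, duration and severity. All of this stands. A reader might infer that patients are unmonitored during the infusions, or that the trial cannot show infusion-related hypotension or bradycardia; the documents support neither. Nor do they restrict the sustained abnormalities of Sections 3.2 and 3.3 to scheduled readings. What the reply does not supply is a statement that the monitored values are outcome data.

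A reader might also infer from the pilot that the schedule catches the placebo peaks, misses the tariquidar peaks, and so is biased toward no difference. That asymmetry exists only if pilot times run from the end of ondansetron. From its start, the placebo maxima are missed too, by 15 minutes, and Section 2.2 does not fully state the origin. Even on the favourable clock it fails for systolic pressure: at 120 minutes the placebo mean is +8.6 mmHg and the tariquidar-session change cannot exceed 5.7 mmHg in size, so a difference of at least 8.6 − 5.7 = 2.9 mmHg is still sampled. The pilot also pools three doses in 8 participants, with every SD larger than its mean.

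The volunteer events are limited evidence as well. The hypotension and bradycardia occurred at 8 mg/kg, twice this trial's dose. The orthostatic case came from a study of 4, 6 or 8 mg/kg, with its dose not given, and that study reported no significant change in heart rate, blood pressure or ECG during or after tariquidar.

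Finally, pulse oximetry or the 3-lead ECG may well supply heart rate. That makes recording it easy, but the outcome still does not name it.

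**Conclusion.** The point holds as a gap in the defined outcome, not in patient safety. There is a 75-minute interval from the start of tariquidar to the first post-baseline outcome reading, with none inside either infusion, and heart rate is unnamed. The vital-sign comparison between sessions therefore cannot describe changes during the infusions, although adverse-effect reporting could. This rests on the pre-infusion reading being taken before tariquidar, as Section 2.4.5.1 and Table 1 indicate, and on Section 3.6 values not being outcome data. The latter is read from the documents' silence; the case report form is not among them.

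The pilot maxima are weak supporting evidence. They do not establish that the comparison understates a tariquidar effect, nor by how much. The change is worth making because it is cheap and concerns a primary outcome.

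**What to change.** In Section 2.4.5.1 and the case report form:

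1. Record blood pressure, heart rate and SpO2 from the Section 3.6 monitor just before ondansetron starts, at the end of ondansetron and at the end of tariquidar (minutes 30, 45 and 60 from tariquidar start).
2. Add one reading between 60 and 120 minutes after ondansetron ends, taken immediately before the repeat CPM and WUR testing. Section 2.4.3 places that testing 90 minutes after the end; its cold-water, heat and pinprick stimuli could alter blood pressure and heart rate, so the reading should not be taken during or just after it.
3. Name heart rate as an outcome vital sign.
4. Compare sessions on change from same-session baseline, including these times.
5. Reconcile Sections 2.4.3, 2.4.5.1 and 3.6 on which monitored values are recorded and analysed.

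All added times lie within the Section 3.6 monitoring window. The cost is a few more form rows per session and cuff readings timed to fixed points, since Section 3.6 sets no interval. Patient care does not change.
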